9.4.4 SAFETY ANALYSES

Safety will be reported by treatment arm using descriptive statistics (means and standard deviations or frequencies and counts) and assessed by comparing the adverse events in the treatment group using Type I error of 5% (2-sided); no control for multiplicity will be done for safety outcomes. We will consider Wilcoxon rank sum tests or two-sample t-tests for continuous outcomes and the exact binomial distribution for proportions.

9.4.5 BASELINE DESCRIPTIVE STATISTICS

Baseline characteristics (including demographic, lab, and clinical variables) will be presented by treatment group (camostat mesylate and placebo). Means and standard deviations will be presented for continuous variables and frequencies and proportions will be presented for categorical variables. No inferential statistics will be presented.

9.4.6 PLANNED INTERIM ANALYSES

Interim monitoring for safety, efficacy and futility will be conducted. When 50% of the participants have accumulated the primary endpoint, we will conduct an interim analysis to assess for efficacy and futility using the group sequential method with asymmetric boundaries. We will use a Pocock boundary for efficacy and will consider stopping early for efficacy if the t-statistic for the treatment effect is greater than the critical value of 1.875; we propose stopping for futility if the drug is trending in the wrong direction, and have set a futility boundary value of -1. Safety will be assessed by comparing the rate of adverse events in the treatment group using Type I error of 5% (2-sided); no control for multiplicity will be done for safety outcomes.

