9.2 SAMPLE SIZE DETERMINATION

The sample size calculation is based on the primary outcome of interest: change in \log_{10} respiratory (nasopharyngeal swab, saliva swab RT-PCR) viral load from baseline to day 4 post-randomization. Given the limited data on the variability of the change in \log_{10} viral load, we have powered the study based on detecting a moderate standardized effect size of 0.3 using an analysis of covariance (ANCOVA), adjusting for baseline \log_{10} viral load. To put into context, one scenario that would produce a 0.3 standardized effect size would be a change of 4 in \log_{10} viral load in the camostat mesylate group compared to a change of 1 in \log_{10} viral load in the placebo group assuming a standard deviation of 5.0. (NOTE: For ANCOVA, the effect size is the standard deviation of the treatment means divided by the pooled standard deviations of the observations.) To be conservative we assume a R-squared of 0 between the \log_{10} viral RNA at 4-days and baseline \log_{10} viral RNA. With a power of 90%, and a type I error rate of 10% (2-sided), we would be able to detect the hypothesized 0.3 standardized effect size with 98 total patients - 49 patients per group with a 1:1 randomization. Increasing this sample size by 15%, 5% for an efficacy and futility look at 50% information (i.e. when half of the patients have been enrolled) and 10% to account for loss to follow up, gives a total of 114 participants (57 per treatment arm).

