9.4.2 ANALYSIS OF THE PRIMARY EFFICACY ENDPOINT(S)

The primary analysis will be according to intent-to-treat and conducted using ANCOVA, adjusting for baseline \log_{10} viral load (or conversion from Ct value assuming $1 \log_{10} = 3.3$ Ct units). We will use the t-statistic for the treatment effect to determine whether the treatment is statistically different from the placebo at the overall 10% level of significance, controlling for baseline \log_{10} viral load. Because of the interim analysis (see below), a p-value of 0.06 (2-sided), corresponding to an efficacy boundary value of 1.875 at the last look, will be used for the level of significance for the primary outcome at the final analysis. In sensitivity analyses, we will also adjust for age and time since onset of symptoms. We will also conduct a per-protocol analysis as a secondary analysis. We will assess the missing mechanism and the impact of missing data. Sensitivity analyses under either missing at random or missing not at random will be considered, as appropriate.

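### The efficacy boundary of 1.875 is a normal-scale constant applied to a t-statistic, so it does not match the final p of 0.06 and benefit-side error is slightly above 5%

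*Combined protocol and SAP*

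**What the plan says.** Section 9.4.2 bases the primary test on the ANCOVA: "We will use the t-statistic for the treatment effect". The aim is to judge whether camostat is "statistically different from the placebo at the overall 10% level of significance". Because of the interim look, the final analysis then uses "a p-value of 0.06 (2-sided), corresponding to an efficacy boundary value of 1.875 at the last look".

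Section 9.4.6 describes one interim, at half of the primary endpoint data, "using the group sequential method with asymmetric boundaries". With a Pocock boundary for efficacy, an early stop is to be considered when the treatment t-statistic is "greater than the critical value of 1.875". On the other side they "have set a futility boundary value of -1".

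The plan does not say that 1.875 is a normal-scale value, which of the two forms (p of 0.06 or boundary of 1.875) governs the final look, or whether the futility boundary is binding.

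**The concern.** A Pocock constant is derived for normally distributed statistics. The plan compares it directly with a t-statistic, and at the interim that t rests on only about 50 participants. The t distribution has heavier tails, so the same cut-off is easier to cross by chance than the design intends. The final rule is also given in two forms that agree only on the normal scale, and there only after rounding.

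These are the thresholds for stopping early and for the primary conclusion, and section 2.1 makes further development of the drug depend on that conclusion. If the final t falls between the two forms, someone must choose the rule after seeing the result.

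**Working it through.** **Inputs.** Overall two-sided level 10% (sections 9.2 and 9.4.2); two looks, the first at 50% (section 9.4.6); boundary 1.875 and final p of 0.06 (section 9.4.2); 98 participants for the fixed design and 114 in total (section 9.2). I take equal arms, an interim at half of the final number, and one covariate, so df = N − 3. That gives 49 − 3 = 46 to 57 − 3 = 54 df at the interim and 98 − 3 = 95 to 114 − 3 = 111 df at the end.

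**Step 1: reproduce the plan's constant.** For two equally spaced looks the interim and final statistics have correlation √0.5. Solving 1 − P(|Z1| < c, |Z2| < c) = 0.10 gives c = 1.8754, with nominal two-sided normal p = 0.0607. The upper-side version, 1 − P(Z1 < c, Z2 < c) = 0.05, gives the same c. So 1.875 is the normal-theory Pocock value and carries 5% on the benefit side. The normal p at exactly 1.875 is 0.0608. The normal value for p = 0.06 is 1.881, so part of the mismatch is rounding.

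**Step 2: put 1.875 on the t scale.** Two-sided p = 2 × P(T > 1.875).

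| Look | df | p at t = 1.875 | t for p = 0.06 | t for p = 0.0607 |
|---|---|---|---|---|
| Interim | 46 | 0.0671 | 1.928 | 1.923 |
| Interim | 54 | 0.0662 | 1.921 | 1.916 |
| Final | 95 | 0.0639 | 1.904 | 1.898 |
| Final | 111 | 0.0634 | 1.900 | 1.895 |

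At the end, |t| from 1.875 to 1.900–1.904 meets the boundary but not p < 0.06. Under the null, the final statistic falls in that gap with probability 0.0639 − 0.06 = 0.0039 (95 df) or 0.0634 − 0.06 = 0.0034 (111 df).

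**Step 3: error over both looks.** I simulated the joint interim and final t-statistics under no effect, with 4 million trials for each of N = 98 and N = 114. The simulated rule is the plan's: stop for efficacy on the upper side only at the interim, then a two-sided final test.

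| Rule | Benefit side | Two-sided, futility non-binding | Two-sided, futility binding |
|---|---|---|---|
| t > 1.875 at the interim, absolute t > 1.875 at the end | 5.3–5.4% | 8.5–8.6% | 6.0–6.1% |
| t > 1.875 at the interim, p < 0.06 at the end | about 5.2% | about 8.2% | about 5.8% |
| Nominal p of 0.0607–0.0608 on the actual df at both looks | 5.0% | about 8.1% | 5.6–5.7% |

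Treating the futility boundary as binding does not change the benefit-side figures at this precision, because a trial at t < −1 at half information almost never ends above 1.875.

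**Step 4: power.** At the plan's effect (f = 0.3, that is, a mean difference of 3 on an SD of 5, or 0.6 SD), moving from 1.875 at both looks to the p-value rule lowers power from 87.9% to 87.4% at N = 98 and from 91.9% to 91.5% at N = 114.

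**The case against.** The best defence is that nothing of substance turns on this. Group-sequential constants are customarily quoted on the normal scale. The normal p for 1.875 is 0.0608, which rounds to 0.06, and section 9.4.2 can be read as letting the p-value govern the final look. The plan states 10% two-sided and never names a 5% limit for the benefit side. The interim is not automatic: section 9.4.6 speaks only of considering a stop, and an independent DSMB reviews the data under a charter that is not among the documents. In a phase IIa trial run at a liberal level, an excess of 0.2 to 0.4 points on one side changes little.

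Much of this stands, and it sets the size of the point. It does not remove the inconsistency. Even if the p-value governs at the end, section 9.4.6 still applies 1.875 to a t-statistic at the interim, and benefit-side error is still about 5.2%.

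A reader might go further and infer that overall error exceeds the stated 10%. The documents do not support that. Values of 10.4% to 10.8% arise only if the interim also rejects for t below −1.875. Section 9.4.6 describes asymmetric boundaries, with efficacy on the upper side and futility on the lower, so a result in the wrong direction at the interim is not a rejection.

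**Conclusion.** The plan is wrong as written, in a minor way. It applies a normal-scale constant to a t-statistic and states two final rules that disagree for |t| between 1.875 and about 1.90. Benefit-side error is about 5.2% to 5.4%, against the 5% that the constant is built to give. Overall two-sided error stays below the stated 10%: about 8.2% to 8.6% if futility is non-binding and about 6% if it is binding.

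The error figures assume df = N − 3, equal arms, an interim at half of the final number and 98 to 114 analysed. If the planned 10% is lost, 114 × 0.9 ≈ 103 are analysed, and the results lie within the ranges given. The disagreement between the two final rules does not depend on the sidedness of the interim or on whether futility is binding.

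**What to change.** In sections 9.4.2 and 9.4.6, state one governing efficacy rule for both looks: a nominal two-sided ANCOVA p below 0.0607, in favour of camostat for an efficacy claim, computed from the t distribution on the degrees of freedom of that analysis. At the planned sizes this is t of about 1.92 at the interim and about 1.90 at the end. Remove 1.875 as a cut-off for t and remove the rounded 0.06. If 1.875 is kept for reference, label it as the normal-scale value from which 0.0607 comes.

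The cost is wording in two sections and about half a point of power. The sample size need not change.

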9.4.7 SUB-GROUP ANALYSES

Not applicable

9.4.8 TABULATION OF INDIVIDUAL PARTICIPANT DATA

Not applicable

9.4.9 EXPLORATORY ANALYSES

Exploratory endpoints will include area under the \log_{10} viral RNA curve; time to complete absence of symptoms the components of the symptom assessment scale (e.g. nose, throat, cough); and hospitalization. Also we are going to use Quidel's Sofia's antigen detection test in this study. Area under the curve (AUC) will only be calculated for participants with at least three follow-up \log_{10} viral load measurements, and will account for the follow-up time. Mean AUC values will be compared using a two-sample t statistic. Time to complete absence of symptoms will be analyzed using the Cox model and event-free rates determined by Kaplan-Meier. Individuals will be administratively censored at 28 days. Those who die will be censored at time of death. We will conduct sensitivity analyses using death as a semi-competing risk. Twenty-eight day hospitalization rates will be compared using an exact binomial distribution. We will also consider additional biomarkers (using similar methods as described for the primary and secondary outcomes) and the individual components of the symptoms (using similar methods as described above).

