6.4 STUDY INTERVENTION COMPLIANCE

The study design is built around obtaining respiratory swabs and saliva from participants. To encourage compliance with study protocol, study drug/placebo will be provided every other day (prior to swabbing and saliva collection) and verbal assessment of whether study drug/placebo was taken as prescribed will be done.

Participants will have the option of not being swabbed again or providing saliva, even after receiving study drug, but lack of day 0 and 4 NP swabs would be a protocol deviation although they would be retained in intention to treat analysis. NP swabs are required at days 0, 4, 14, 28; optional swabs at days 2 and 6. Saliva will be collected at all study visits.

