7 STUDY INTERVENTION DISCONTINUATION AND PARTICIPANT DISCONTINUATION/WITHDRAWAL

7.1 DISCONTINUATION OF STUDY INTERVENTION

Reasons why a study subjects may be withdrawn from the study intervention include, but are not limited to:

- Subject request (withdrawal of consent)
- Protocol violation, i.e. declining to take drug or be swabbed or providing saliva for viral load two times.
- AE or reactions
- Any condition, interaction, or contraindication where continued participation in the study will result in an unacceptable risk for the subject, as assessed by the Investigators or advisers
- Discontinuation of the study by the Sponsor
- Lost to follow-up

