8 STUDY ASSESSMENTS AND PROCEDURES

8.1 EFFICACY ASSESSMENTS

Biological specimen collection and laboratory evaluations.

On study days 0, 2 (NP swab optional, saliva required), 4 (NP swab and saliva both required) and 6 (NP swab optional, saliva required), 14+/-2 (NP swab and saliva both required) and 28+/-2, (NP swab and saliva both required), samples will be obtained and analyzed by an FDA-authorized COVID-19 RT-PCR assay coordinated through the YNHH Clinical Virology Laboratory, and Yale Department of Pathology. Additional testing including antigen detection may be done on an NP swab, nasal swab or saliva.

On study days 0, 14+/-2 and 28+/-2, blood will be collected for 1) clinical surveillance→complete blood count, blood chemistries and coagulation including electrolytes, BUN, creatinine, AST, ALT, total and direct bilirubin, HS-CRP, LDH and alkaline phosphatase, PT, INR, d-dimer, fibrinogen; 2) research testing including obtaining serum, plasma and peripheral blood mononuclear cells for research studies. A maximum of 125 mL of blood will be requested to be collected on days 0, 14 and day 28 (total of 375 mL over four weeks) for these purposes.

Respiratory swab and saliva RT-PCR testing will be done by YNHHS or YNHHS-designated send-out laboratories. Quidel's Sofia platform will be use at the study site for antigen detection. Positivity and Ct values will be recorded and \log_{10} viral loads back-extrapolated from \log_{10} being equivalent to 3.3 Ct units or as determined using a concomitant standard curve.

Camostat mesylate in COVID-19 Outpatients

Protocol #2000027971

Version 8.0
18 August 2020

Blood chemistries and CBCs (and an FDA-approved POC urine pregnancy test will be done on site prior to enrollment for appropriate women as required) will be done by YNHHS laboratories and recorded, and results reported to patients.

Remaining blood samples will be stored in a biological specimen repository approved by Yale University as follows:

Investigator: [name]
Type of Review: Modification/Update
Title of Study: Specimen Repository for Hematologic Diseases
IRB Protocol ID: 1401013259
Submission ID: MOD00029770
Committee Name: IRB 0-Ad Hoc Committee

Final Approval Date: 3/29/2020

Expiration Date: 2/17/2021

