9.4.3 ANALYSIS OF THE SECONDARY ENDPOINT(S)

Secondary outcomes of interest include: change in \log_{10} respiratory (nasopharyngeal swab, saliva RT-PCR) viral load from baseline (day 0) to days 2 and 6 post-randomization; \log_{10} and risk for a positive COVID-19 test at day 6, 14 and 28; and change of COVID-19 symptom score from baseline (day 0), as measured at days 6 and 14 +/- 2 days after enrollment (day 0). The same ANCOVA analysis as proposed for the primary endpoint will be used to analyze two and six day change in \log_{10} for the secondary endpoint. Risk for positive COVID19 test at day 6, 14 and 28 will be compared using an exact binomial distribution. Linear mixed models will be used to describe trajectories of change in the symptom score. The models will include fixed effects for treatment, time and the interaction of treatment and time. An unstructured covariance pattern will allow for correlation between repeated observations. Differences in means at each timepoint will be estimated along with 90% confidence intervals. All statistical tests will be conducted at 10% level of significance (two-sided) with no adjustment for multiple testing.

The COVID-19 PRO daily self score tool, derived almost entirely from a validated influenza symptom scoring. Tool (FLU-PRO)10 consists of 39 items that are answered daily. Items 1-33 are Likert scale questions (rated 0-4) where 0 = not at all, 1, 2 and 4 = very much. These items are summed to score the severity of symptoms- where a total score of 132 would indicate the greatest severity of symptoms and a score of 0 would indicate no severity of symptoms. Items 34-38 are also Likert scale questions (rated 0-4) that measure the frequency of specific daily symptoms where 0 = 0 times and 4 = 4 times or more. These items are summed to score the frequency of symptoms- where the highest score for the frequency of symptoms (20) indicates the greatest burden of symptom frequency. The last question (39) asks patients for their highest temperature in Fahrenheit.

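### The exploratory viral-load AUC is limited to participants with three or more follow-up values, with no specimen named and baseline unused; how many this excludes depends on the specimen

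*Combined protocol and SAP*

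**What the plan says.** Section 9.4.9 lists the area under the log10 viral RNA curve as an exploratory endpoint. The eligibility rule is that "Area under the curve (AUC) will only be calculated for participants with at least three follow-up" log10 viral load measurements; the same sentence adds that follow-up time will be taken into account. The test is given as "Mean AUC values will be compared using a two-sample t statistic". The section plans no analysis for participants whom the rule leaves out.

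The rule names no specimen. Elsewhere the viral-load outcome is "respiratory (nasopharyngeal swab, saliva RT-PCR" (Section 9.4.3), with the two specimens listed together.

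The two specimens are collected on different schedules. Section 6.4 says "NP swabs are required at days 0, 4, 14, 28; optional swabs at days 2 and 6", then "Saliva will be collected at all study visits". Section 8.1 agrees; its entry for day 6, for example, reads "6 (NP swab optional, saliva required", and day 2 is treated in the same way.

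Sampling is voluntary after treatment starts: "Participants will have the option of not being swabbed again or providing saliva, even after receiving study drug" (Section 6.4). Section 7.1 lists, among the reasons for withdrawal from the intervention, "declining to take drug or be swabbed or providing saliva for viral load two times".

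**The concern.** Whether a participant has an AUC is decided by what happens after randomisation: attending, agreeing to be sampled, and being well enough to do both. Randomisation protects the comparison of everyone assigned, not of those who later supply three values. If supplying samples is related both to arm and to the viral course, the difference in mean AUC among those included need not equal the difference among all randomised.

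The rule is also uneven across participants. Three nasopharyngeal follow-up swabs are required and three are needed. A participant who takes no optional swabs is dropped after one miss, while one who agrees to all five can miss two. Values at days 2, 4 and 6 qualify just as well as values at days 4, 14 and 28. Adjusting for follow-up time puts these on a common scale, but they still describe different stretches of the infection, and the adjustment cannot bring back anyone excluded.

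The AUC is also handled less carefully than related outcomes. Sections 9.4.2 and 9.4.3 adjust the day 2, 4 and 6 changes for baseline log10 viral load; the AUC comparison does not, although Section 4.2 describes viral burden running from 10^2 to 10^9 per swab. The missing-data sensitivity analyses in Section 9.4.2 are written for the primary endpoint and are not extended to the AUC.

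At stake is the reliability and precision of one exploratory summary of the whole viral course.

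**Working it through.** **Plan's own figures.** The plan gives no figure for how many participants will have an AUC, so there is none to reproduce. The planned total of 114 (Section 9.2) serves only as a denominator. It reproduces: 98 x 1.15 = 112.7, rounded up to 113 and then to 114 for equal arms.

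**Inputs from the documents**
- Values needed: at least 3 (Section 9.4.9).
- Required nasopharyngeal follow-up: days 4, 14 and 28, so 3; days 2 and 6 optional (Sections 6.4, 8.1).
- Required saliva follow-up: days 2, 4, 6, 14 and 28, so 5 (Sections 6.4, 8.1).

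**Assumptions.** The documents give no per-visit completion rate and no uptake of optional swabs. Let p be the probability that a scheduled sample yields a value, independent across visits, and take p = 0.95 and 0.90.

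**Nasopharyngeal, required swabs only.** All three must be present, so the share excluded is 1 - p^3.
- p = 0.95: 1 - 0.8574 = 14.3%
- p = 0.90: 1 - 0.7290 = 27.1%

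**Nasopharyngeal, half of the optional swabs taken.** Each optional swab yields a value with probability r = p/2. The share retained is p^3 + 3p^2(1 - p)[1 - (1 - r)^2] + 3p(1 - p)^2 r^2.
- p = 0.95, r = 0.475: 0.8574 + 0.1354 x 0.7244 + 0.0071 x 0.2256 = 0.957, so 4.3% excluded
- p = 0.90, r = 0.45: 0.7290 + 0.2430 x 0.6975 + 0.0270 x 0.2025 = 0.904, so 9.6% excluded

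**Saliva.** Exclusion needs fewer than 3 of 5 values: 10p^2(1 - p)^3 + 5p(1 - p)^4 + (1 - p)^5.
- p = 0.95: 0.12%
- p = 0.90: 0.0081 + 0.00045 + 0.00001 = 0.86%

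| Curve | Excluded, p = 0.95 | Excluded, p = 0.90 | Retained of 114 |
|---|---|---|---|
| Nasopharyngeal, required swabs only | 14.3% | 27.1% | 98; 83 |
| Nasopharyngeal, half of optional taken | 4.3% | 9.6% | 109; 103 |
| Saliva | 0.12% | 0.86% | 114; 113 |

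**Clustered missingness.** Missed visits may cluster in the same people. As a rough check, suppose that the 10% loss to follow-up allowed for in Section 9.2 all occurs before three values exist, and p = 0.90 in the rest. Retention is then 0.9 x 0.729 = 65.6% (75 of 114) for required nasopharyngeal swabs only, and 0.9 x 0.9914 = 89.2% (102 of 114) for saliva. The gap between specimens remains, but the saliva loss is no longer negligible.

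These figures count exclusions. They do not measure bias.

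**The case against.** The strongest reply is that the rule may exclude almost nobody. Saliva is required at every follow-up visit, viral load is defined with saliva included, and Section 9.4.9 does not confine the curve to swabs. With five required values and three needed, independent misses at 5-10% cost under 1% of participants. The 14-27% needs a nasopharyngeal curve, no optional swabs, and a miss rate that the documents do not supply. This stands, and it is why the point has to be conditional on the specimen. It does not settle the matter for the plan, because the section leaves the specimen open and Section 4.2 calls the nasopharyngeal swab the reference standard.

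Several further replies stand at least in part. A minimum number of points for a per-person AUC is conventional. Follow-up time is to be accounted for. An unadjusted t-test is valid under randomisation, so baseline adjustment improves precision and does not correct an error. Blinding limits refusal driven by knowledge of the arm, though not refusal driven by illness.

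A reader might infer that the rule removes a large share of participants, or that it invalidates the randomised comparison. The documents support neither. The first ignores saliva and the unknown uptake of optional swabs. The second needs missingness related to both arm and outcome, and nothing in the documents bears on that.

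**Conclusion.** The point holds as a limited one. The AUC analysis selects on post-randomisation sampling, leaves available baseline information unused, names no specimen and has no planned check on those excluded. At an assumed independent miss rate of 5-10% per visit, the share excluded ranges from about 0.1-0.9% (saliva) through about 4-10% (nasopharyngeal, half of the optional swabs taken) to 14-27% (nasopharyngeal, required swabs only). Which of these applies cannot be settled from the documents, nor can the direction or size of any bias.

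The endpoint is exploratory. The day 4 primary analysis and the sample size do not depend on it, and Section 6.4 keeps participants without the day 0 and day 4 swabs in the intention-to-treat analysis. The case for change is better precision and a weaker missing-data assumption at little cost. Label: cheap improvement.

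**What to change.** In Section 9.4.9:

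1. Make the main AUC comparison a weighted sum of visit means from a mixed model for repeated log10 viral load, adjusted for baseline log10 viral load and including all randomised participants with any measurement. Section 9.4.3 already specifies a model of this kind, with unstructured covariance, for symptom scores.
2. Fix the weights in advance. Trapezoidal weights on the scheduled days 0, 2, 4, 6, 14 and 28 are 1, 2, 2, 5, 11 and 7, which sum to 28.
3. Run the analysis separately for nasopharyngeal swab and saliva.
4. State the value or censoring rule for undetectable results, and that they count as measurements. Days 14 and 28 carry 11 + 7 = 18 of the 28 units of weight, and the plan itself compares positivity on those days, so this rule could matter to the result.
5. Keep the t-test in participants with three or more values as a sensitivity analysis, and report the numbers excluded by arm.

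The cost is a little more analysis work; no extra samples or visits are needed. The model relies on data being missing at random given the observed values. That is an assumption, but a weaker one than the t-test needs, which is that excluded participants resemble those included.

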1.3 SCHEDULE OF ACTIVITIES (SOA)

Procedures	Enrollment, Study Visit 1, Day 0	Study Visit 2 Day 2	Study Visit 3 Day 4	Study Visit 4 Day 6	Study Visit 5 Day 14+/- 2 days	Study Visit 6 Day 28+/- 2 days
Informed consent	X					
Demographics	X					
Medical history	X					
Randomization	X					
Administer study intervention: Subjects receive two days worth of drug/placebo on days 0, 2, 4 and one day of drug/placebo on day 6	X Drug/placebo For 2 days	X Drug/placebo For 2 days	X Drug/placebo For 2 days	X Drug/placebo For 1 day		
Nasopharyngeal swabs, saliva for COVID-19 RT-PCR and antigen testing	X	X Swabs optional	X	X Swabs optional	X	X
Physical exam: Vital signs, wt, pulse oximetry, other as clinically indicated	X	X	X	X	X	X
Urine pregnancy test (as indicated)	X					
Blood pregnancy test (as indicated)					X	
Hematology and coagulation	X				X	X
Blood chemistries	X				X	X
Adverse event review and evaluation	X	X	X	X	X	X
Concomitant medication review	X	X	X	X	X	X
Blood for research biorepository	X				X	X
Complete Case Report Forms (CRFs)	X	X	X	X	X	X

All subjects, regardless of study arm (blinded to subjects and investigators), will be tracked for their health status through daily phone calls from days 0 to day 14 with routine, scheduled daily phone calls by study staff to help participants fill out symptom scores on the standardized COVID-19-PRO instrument. Any subject reporting concerning symptoms, particularly chest pain, shortness of breath, extreme prostration, change in mental status will be referred to for emergency care. Subjects will be given a contact phone number of PI or designee to contact for any concerns. If there is complete resolution of symptoms at the day 14 visit, then phone calls will not be routinely continued by our study staff but subjects will be encouraged to call PI or designee for concerns or discussions.

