9.4 STATISTICAL ANALYSES

9.4.1 GENERAL APPROACH

All primary analyses will be performed as intent-to-treat analyses with a type I error rate of 10% (two-sided). Parametric distributional assumptions will be checked. If assumptions fail, other distributions will be considered prior to transformations and non-parametric methods. SAS (version 9.4) or the latest version of R (currently 3.6.3) will be used to analyze the data.

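### The Cox model for time to complete absence of symptoms names no baseline covariate; adding the day-0 symptom score, already collected, would gain power if that score is prognostic

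*Combined protocol and SAP*

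**What the plan says.** Section 9.4.9 gives the analysis in one sentence: "Time to complete absence of symptoms will be analyzed using the Cox model and event-free rates determined by Kaplan-Meier". It then adds "Individuals will be administratively censored at 28 days" and censors deaths at the time of death. It names no covariate and no significance level, and it does not say which measurement defines complete absence of symptoms. Its closing sentence about using similar methods concerns biomarkers and individual symptom components, so it brings no covariate into this model.

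The day-0 score exists. Section 1.3 provides, from day 0 to day 14, "routine, scheduled daily phone calls by study staff to help participants fill out symptom scores on the standardized COVID-19-PRO instrument". Section 9.4.3 uses day 0 as the reference for the secondary symptom endpoint, described as "change of COVID-19 symptom score from baseline (day 0), as measured at days 6 and 14". The severity part of the instrument (items 1-33) is summed to a total between 0 and 132.

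Elsewhere the plan states baseline adjustment when it wants it. Section 9.4.2 says "The primary analysis will be according to intent-to-treat and conducted using ANCOVA, adjusting for baseline" log10 viral load, and Section 9.4.3 carries the same ANCOVA to days 2 and 6. Age and time since symptom onset are named only for the sensitivity analysis of the primary endpoint. Section 3 lists clinical outcome as a tertiary objective that the study is not powered for.

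**The concern.** The natural reading of Section 9.4.9 is a Cox model with treatment alone. A participant with many or severe symptoms on day 0 plausibly takes longer to become free of them, so the day-0 score is an obvious candidate covariate. Baseline spread may be wide. Section 5.1 admits people with a single compatible symptom, or with a recent high-risk exposure, and Section 4.1 has no stratification. With 57 per arm, the chance difference between arms in mean day-0 score has a standard error of sqrt(2/57) = 0.19 SD.

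In a Cox model, omitting a prognostic covariate has two effects even under perfect randomization. The test loses power. The hazard ratio being estimated also becomes a marginal one, which lies closer to 1 than the hazard ratio conditional on the covariate. At stake is how much a small trial can say about speed of recovery, which could inform the later clinical-endpoint trial that Section 3 envisages. If the section is read as merely silent, the choice of covariates is left open until after the data are seen.

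**Working it through.** **The plan's own figure.** The protocol gives no power, hazard ratio or event count for this endpoint. Its only computed figure is the sample size for the primary endpoint (Section 9.2). The worked example has changes of 4 and 1 with SD 5.0, so f = 1.5/5 = 0.30. At two-sided 10%, the noncentral F distribution gives power 0.8985 for N = 96 and 0.904 for N = 98, so 98 reproduces. Adding 15% gives 49 x 1.15 = 56.35 per arm, hence 57 per arm and 114 in total. The check below uses N = 114.

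**Inputs from the protocol.** N = 114, 1:1 allocation, 10% loss to follow-up (Section 9.2); censoring at day 28 (Section 9.4.9); two-sided 10%, carried over from Section 9.4.3, where "All statistical tests will be conducted at 10% level of significance (two-sided) with no adjustment for multiple testing".

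**Inputs that are assumptions.** Weibull times with shape 1.3, placebo median 10 days, conditional treatment hazard ratio 1.25 to 2.0, and a standard normal day-0 score. Its log-hazard ratio is 0.2 to 1.0 per SD, a higher score meaning slower resolution. A value of 0.2 multiplies the hazard of resolution by exp(-0.2) = 0.82 per SD; 0.7 multiplies it by 0.50; 1.0 by 0.37.

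**Method.** Each setting had 3,000 simulated trials, each fitted with treatment only and with treatment plus score.

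Power (%) without -> with the score; gains were taken before rounding:

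| log-HR per SD | HR 1.5, day 28 | HR 1.75, day 28 | HR 1.5, day 14 | HR 1.75, day 14 |
|---|---|---|---|---|
| 0.2 | 63 -> 66 (+3) | 86 -> 88 (+2) | 55 -> 57 (+1) | 79 -> 80 (+1) |
| 0.3 | 62 -> 67 (+5) | 85 -> 89 (+4) | 52 -> 55 (+3) | 77 -> 80 (+3) |
| 0.5 | 53 -> 65 (+12) | 78 -> 87 (+10) | 48 -> 56 (+8) | 74 -> 81 (+8) |
| 0.7 | 47 -> 65 (+18) | 70 -> 88 (+17) | 41 -> 55 (+15) | 66 -> 79 (+14) |
| 1.0 | 37 -> 61 (+25) | 59 -> 85 (+27) | 36 -> 53 (+17) | 52 -> 77 (+25) |

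The day-14 columns apply if usable symptom data effectively end when the scheduled daily calls do.

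**Other treatment effects, day 28.** Across the five strengths the gains are 2, 3, 5, 7 and 11 points at HR 1.25, and 1, 2, 5, 12 and 21 points at HR 2.0.

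**No prognostic effect.** With log-HR 0 the two analyses differ by no more than about 0.4 point.

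**Hazard ratio.** With a conditional value of 1.5 and censoring at day 28, the mean unadjusted hazard ratio is 1.49, 1.48, 1.41, 1.39 and 1.31 for the five strengths. With 1.75 it is 1.74, 1.70, 1.61, 1.55 and 1.46.

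**Hand check with the Schoenfeld formula.** Power = Phi(sqrt(D/4) x ln HR - 1.645), where D is the number of events. Take HR 1.75, log-HR 0.7 per SD, day 28, D = 101, so sqrt(101/4) = 5.025.
- Conditional hazard ratio: 5.025 x ln 1.75 - 1.645 = 5.025 x 0.5596 - 1.645 = 1.167, power 88% (simulated 87.6%).
- Marginal hazard ratio 1.55: 5.025 x 0.4383 - 1.645 = 0.557, power 71% (simulated 70.3%).

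The power loss is thus accounted for by the hazard ratio moving from 1.75 to 1.55.

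**Type I error.** With treatment HR 1.0 the rejection rate is near 10% either way. For day-14 censoring it is 8.6% to 10.4% without the score and 8.8% to 10.4% with it.

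**The case against.** Several objections stand in part.

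- **The size is not in the protocol.** A reader might infer a fixed loss, say 5 to 20 points. That cannot be supported: Section 9.4.9 gives no hazard ratio, event rate or prognostic strength, and the result runs from nothing to 27 points over the assumed range. The simulation also favours adjustment, because its covariate is normal and enters the model correctly. The real score is a bounded sum, and people admitted on exposure alone may score 0.
- **The score may predict weakly.** A reader might assume that the event is the COVID-19-PRO reaching zero, which would tie the two together. Section 9.4.9 does not say so. Complete absence depends on the last symptom to clear, and a low score soon after diagnosis may mean early illness rather than near recovery. This is why a weak covariate belongs in the range.
- **A smaller hazard ratio is not bias.** A reader might take attenuation toward 1 as an error in the unadjusted analysis. It is not: that model estimates a marginal hazard ratio and its test is valid. The two models target different quantities.
- **Simple comparisons are consistent within Section 9.4.9.** Viral-load area under the curve gets an unadjusted two-sample t test, and hospitalization an exact binomial comparison. The plan is therefore not contradicting itself by leaving this model unadjusted.
- **Little depends on it.** The clinical objective is unpowered, and symptoms are already analysed at the secondary level with mixed models.

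What remains is that a plausible, already collected covariate is unused, and that naming it in advance costs almost nothing.

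**Conclusion.** The point holds as a conditional one of low severity. Section 9.4.9 names no baseline covariate for this Cox model although the day-0 score is available. If the score is prognostic, the omission costs power and gives a marginal hazard ratio nearer to 1 than the conditional one.

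Under the stated assumptions (N = 114, two-sided 10%, placebo median 10 days), the cost in power is:
- nothing if the score is not prognostic;
- about 1 to 3 points at log-HR 0.2 per SD;
- about 3 to 18 points at 0.3 to 0.7 per SD, for a treatment hazard ratio of 1.5 to 1.75 and follow-up to day 14 or 28;
- more than 20 points at 1.0 per SD in most settings, though less at HR 1.25 (11 points at day 28) or at HR 1.5 with day-14 follow-up (17 points).

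Neither a false-positive problem nor a biased analysis follows, and the planned sample size is unaffected. No power target is missed, because the protocol sets none for this endpoint.

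**What to change.** In Section 9.4.9, pre-specify that time to complete absence of symptoms is analysed with a Cox model containing treatment and the day-0 COVID-19-PRO severity score (items 1-33, continuous). Keep the Kaplan-Meier curves by arm as the unadjusted description, and report the unadjusted hazard ratio as a sensitivity analysis so that both the conditional and the marginal quantity are shown and labelled.

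The cost is one sentence and no new data. There are two small downsides: the main hazard ratio becomes conditional on the day-0 score, and a participant without a day-0 score needs a simple imputation rule, to be stated in the same place.
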